4.2. EXPERIMENTAL PROTOCOL

4.2.1. Study Design

This study will be conducted in a medical clinical specifically adapted for testing and with a permissive playful space to mitigate the stress of the involved children and avoid social conflicts during evaluation sessions. The space will comprise at least 17 individual analysis rooms, and the evaluation will involve 20 neuropsychologists, 2 pediatricians and 1 psychiatrist with prior and ensured training.

Children will be evaluated on DAY 0, DAY 45 and DAY 90 to quantify inflammatory markers through blood collection; for measuring fecal calprotectin, by collecting fecal samples; and finally, for the primary outcomes mentioned in this project: neuropsychological (Vineland-3); psychiatric (ADOS) and psychopedagogical (CARS). After the first data collection, individuals will be randomized to receive the K11-T probiotic mixture or the K11-Tmax probiotic mixture or placebo, in a 1:1:1 ratio. After the initial 90-day follow-up, up to 30% of the sample using K11-Tmax will continue to be monitored, being re-evaluated after 365 days in all aspects mentioned. Children will be stratified by age, gender and level of support (see Appendix B) and then randomized to intervention according to the groups below.

Condition or Disease	Intervention/Treatment	Phase
Children with ASD	Drug 1: Probiotic K11-T Drug 2: Probiotic K11-Tmax Drug 3: Placebo	Phase 3

4.2.2. Research Arms

Groups	Intervention/Treatment
Group 1	Probiotic K11-T 1 dose/day Orally
Group 2	Probiotic K11-Tmax 1 dose/day Orally
Group 3	Placebo 1 dose/day Orally

4.2.3. Quantification of C-reactive Protein (CRP)

For the quantification of PCR, individuals were instructed to fast for 8 hours. Polymerase Chain Reaction (PCR) is a widely used technique for amplifying specific DNA sequences in vitro. It allows selective and rapid amplification of a target DNA region, enabling its detection and analysis. The PCR methodology involves the following steps:

- Reaction preparation: Reaction components are prepared in a reaction tube, including the target DNA, primers (specific oligonucleotides that bind to sequences of interest), nucleotides (DNA building blocks), a DNA polymerase enzyme (which catalyzes DNA synthesis), and a reaction buffer providing optimal conditions for enzyme activity.
- Denaturation: The reaction mixture is heated to a high temperature (usually between 94-98°C) to denature the target DNA, separating the two complementary strands.
- Primer Annealing: The temperature is reduced (usually between 50-65°C) to allow the primers to anneal (bind) to the complementary DNA sequences at the ends of the target.
- Extension: The temperature is then raised again (usually around 72°C) to enable the activity of the DNA polymerase enzyme. The enzyme synthesizes a new complementary DNA strand to each of the original strands.
- Amplification cycles: The denaturation, annealing, and extension steps are repeated in successive cycles. Each cycle doubles the number of copies of the target DNA. The total number of cycles may vary depending on the desired amount of amplification.
- At the end of PCR, multiple copies of the target DNA sequence are obtained, allowing for its subsequent detection and analysis. Amplification can be visualized using various methods such as agarose gel or capillary electrophoresis, and detection can be performed using fluorescent probes, specific dyes, or DNA sequencing.

4.2.4. Serum Cortisol Quantification

For serum cortisol quantification, participants were instructed to fast for 8 hours and ensure that sample collection is done between 7 and 10 am. To measure serum cortisol levels, serum samples will be centrifuged at 2,200 g for 10 minutes at 18°C and stored in gel tubes at a temperature of 2 to 8°C. The analysis will utilize the chemiluminescence method, and the results will be expressed in mcg/dL.

4.2.5. Insulin Quantification

For insulin quantification, individuals were instructed to fast for 8 hours. To measure serum insulin levels, serum samples will be centrifuged at 2,200 g for 10 minutes at 18°C and stored in gel tubes at a temperature of 2 to 8°C. The analysis will utilize the chemiluminescence method, and the results will be expressed in mcU/ml.

4.2.6. Prolactin Quantification

For prolactin quantification, individuals were also instructed to fast for 8 hours. To measure serum prolactin levels, serum samples will be centrifuged at 2,200 g for 10 minutes at 18°C and stored in gel tubes at a temperature of 2 to 8°C. The analysis will utilize the chemiluminescence method, and the results will be expressed in ng/dL.

4.2.7. Fecal Calprotectin Measurement

The sample for fecal calprotectin measurement will be collected by convenience sampling, considering the inherent behavioral difficulties of the disorder, while respecting a minimum sample value of 30% of the total sample of children, totaling at least 81 children. Families will be instructed to collect the first stool of the day and keep it refrigerated at a temperature ranging from 4 to 5 degrees Celsius (in a regular refrigerator) until the evaluation time. Children undergoing colonoscopy, using laxatives or suppositories, or undergoing examinations using radiological contrasts within 72 hours before collection will have their samples discarded. The fecal material will be stored in a refrigerated environment, processed using a specific kit for measurement, and expressed in µg/g.

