4. MATERIALS AND METHODS

The present study will be characterized as a randomized, double-blind, placebo-controlled clinical trial. The sample calculation was based on the current prevalence of ASD in children according to the latest release from the Center for Disease Control, with a target of 270 volunteer participants with ASD, maintaining a confidence interval of 5%.

Pre-screening will have immediate action, and volunteers can register by filling out a virtual recruitment questionnaire available on the website www.gon1.com.br. This phase is crucial in raising sponsorship funds to ensure the feasibility of the research, considering the minimum sample safety requirements. It is emphasized that the analysis of inclusion criteria and contact with families will only be conducted after the project approval by this Research Ethics Committee.

The safety of using the probiotic mix will be ensured by the results obtained from toxicity and pathogenicity tests and by defining the supplement ceiling (zinc 20% 0.148g, selenium 1% 0.032g + magnesium 65mg + vitamin A 0.300g) contained in the K11-Tmax version according to the positive list from ANVISA stratified at the age of 3 years.

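### The fecal calprotectin sample is a convenience subset that is neither fixed before randomisation nor required to be the same children at Day 0, 45 and 90

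*Protocol*

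**What the plan says.** Section 4.2.7 gives the collection rule: "The sample for fecal calprotectin measurement will be collected by convenience sampling". The reason offered is the behavioural difficulty that comes with the disorder. The only size requirement is a floor for the whole trial, "respecting a minimum sample value of 30% of the total sample of children, totaling at least 81 children". No floor is set per arm or per visit, and nothing is said about when the children are chosen or whether the same ones are followed. Samples are lost if a child had a colonoscopy, laxatives, suppositories or radiological contrast: children so exposed "within 72 hours before collection will have their samples discarded". No repeat collection is mentioned.

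Section 4.2.1 sets the visits: "Children will be evaluated on DAY 0, DAY 45 and DAY 90 to quantify inflammatory markers through blood collection". The same sentence continues with stool, "for measuring fecal calprotectin, by collecting fecal samples", and names no subset. On allocation it says: "After the first data collection, individuals will be randomized to receive the K11-T probiotic mixture or the K11-Tmax probiotic mixture or placebo". Allocation is 1:1:1, stratified by age, gender and level of support. The trial target is in Section 4: "with a target of 270 volunteer participants with ASD".

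Calprotectin is the only fecal marker in the inflammatory objective (Section 3). Section 4.2.1 names Vineland-3, ADOS and CARS as the primary outcomes. Section 4.2.11 lists t-tests, ANOVA and repeated-measures tests, with nonparametric counterparts, and no baseline-adjusted comparison.

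**The concern.** Day 0 stool is due before allocation; Day 45 and Day 90 stool comes after it. Because Section 4.2.7 does not tie the later samples to children who gave one at Day 0, its floor could be met by partly different children at each visit. Two things follow.

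- **Selection after allocation.** Whether a child gives a usable later sample could depend on bowel habit or laxative use, and a gut-directed product might change either. The arms compared at Day 90 would then no longer be simply the arms that were randomised.
- **Loss of pairing.** Change from baseline, paired tests, repeated measures and baseline adjustment all need the same child at more than one visit. The rule does not secure that.

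This is more than detail that could be left to an analysis plan. Who gives a sample, and when, is a collection rule that the protocol itself sets, and no later plan can recover a baseline sample that was never taken.

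**Working it through.** **Inputs.** N = 270 (Section 4); minimum fraction 30% (Section 4.2.7); 1:1:1 allocation, hence 90 per arm (Section 4.2.1); alpha 0.05 (Section 4.2.11). Assumed, because the protocol is silent: two-sided testing, 80% power, and differences in SD units from a two-sample t-test without baseline adjustment. The protocol gives no effect size or power for calprotectin, so there is no power figure to reproduce.

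**The plan's own figure.** 0.30 × 270 = 81, which agrees with Section 4.2.7. Split evenly, 81 / 3 = 27 per arm.

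**Bounds on pairing at the floor.** With 81 children sampled at each of two visits, the number sampled at both is at least max(0, 2 × 81 − 270) = max(0, −108) = 0 and at most 81.

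**Points within the bounds.** Let p = 0.30 be the chance that a child gives a sample at a visit, and r the within-child correlation of giving one at Day 0 and at Day 90 (assumed). Then

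expected pairs = 270 × [p² + r × p(1 − p)] = 270 × [0.09 + 0.21r].

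| r | Pairs | Per arm | Detectable difference (SD) |
|---|---|---|---|
| 0 | 270 × 0.090 = 24.3 | about 8 | about 1.5 |
| 0.5 | 270 × 0.195 = 52.7 | about 18 | 0.97 |
| 0.7 | 270 × 0.237 = 64.0 | about 21 | 0.88 |
| 0.9 | 270 × 0.279 = 75.3 | about 25 | 0.81 |
| 1 | 81 | 27 | 0.78 |

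The last column uses the unrounded number per arm. With r = 0 at all three visits, 270 × 0.3³ = 7.3 children would have all three samples.

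**If every child gave stool.** With 90 per arm the detectable difference is 0.42 SD, against 0.78 SD at 27 per arm. Whether stool comes from all children or from a subset therefore matters for what this marker can show.

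**Chance imbalance between arms.** If 81 children are drawn without regard to arm from 90/90/90, the smallest arm has 22 or fewer in about 30% of draws. Comparing 22 with 27 children gives a detectable difference of 0.82 SD instead of 0.78 SD, so this matters little.

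**The case against.** The strongest reply is that Section 4.2.7 counts children, so one followed group is its natural reading, and that 81 is a minimum. The stated reason for convenience sampling is behavioural and probably stable within a child, so those who manage at Day 0 are likely to manage later. This stands. A reader might infer that the Day 0 to Day 90 comparison will be nearly empty. That needs exactly 30% provision together with independence between visits, and the protocol's own reason for the subset points away from independence. The figure of 24 is near the low end of a range and is not a forecast.

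A reader might also infer that the calprotectin comparison is biased, or has lost the protection of randomisation. The documents do not support that. The trial is double-blind, Day 0 collection precedes allocation, and no figure suggests that stool provision or laxative use would differ by arm. Discarding unsuitable samples is an ordinary validity rule. Selection that depends on arm is possible, but its size is unknown.

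Nor does Section 4.2.1 say that all children give stool. It suggests so only by naming no subset, and 4.2.7 is the more specific text. This is wording to align.

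What the reply does not remove is that a followed group is nowhere stated. The text permits later samples from children without a baseline value.

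**Conclusion.** The concern holds in a limited form. Section 4.2.7 leaves open which children give calprotectin samples at which visit and does not fix the set before allocation. This could weaken the randomised comparison and thin the paired data. At the 81-child floor the paired number is bounded only by 0 and 81; about 53 to 75 is expected if within-child correlation is 0.5 to 0.9, and about 24 under independence. These correlations are assumptions, and a larger sample than the floor would raise all the expected figures.

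The consequence is confined to a marker that is not a primary outcome, so this is something the sponsor should change and not a threat to the trial's main conclusions. It is worth acting on because the Day 0 visit already comes before randomisation and the remedy needs no new visit.

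**What to change.** In Section 4.2.7:

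- Define the calprotectin set as all children with a usable Day 0 sample, taken before randomisation, with at least 81 children.
- Seek Day 45 and Day 90 samples from those same children.
- Where the 72-hour discard rule applies, allow a repeat collection if feasible. For Day 0 it must still come before randomisation.
- Compare the randomised arms with the Day 0 value as covariate, and report usable samples by arm and visit. Later samples may still be missing, but against a fixed denominator the losses can be seen by arm.

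In Section 4.2.1, say that stool comes from a subset and refer to 4.2.7.

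If a detectable difference is quoted, give about 0.78 SD as the value for 27 complete children per arm (two-sided 0.05, 80% power), before losses and without baseline adjustment.

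The cost is protocol wording, tracking of the Day 0 set and a few repeat kits. The downside is that children who can give stool only after Day 0 are left out of the main calprotectin comparison.

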4.2.8. Neuropsychological Assessment

Neuropsychological assessment in patients with ASD involves a multidisciplinary approach, considering different aspects of neuropsychological functioning. Standardized analysis will be

conducted using the Vineland Adaptive Behavior Scales - Third Edition (Vineland-3)⁴⁶. The forms will be completed in their self-administered version by parents/caregivers and teachers, under the supervision of a qualified and trained health professional. Vineland-3 assesses adaptive behavior by dividing it into five domains: communication skills, daily living skills, socialization skills, motor skills and maladaptive/behavioral skills of the child. Those responsible will respond to the items in each domain on a scale ranging from 0 to 2, with 0 being never; 1 sometimes and 2 often. To calculate the final score, the scores are transformed into a population average of 100 based on age and a standard deviation of 15 according to the specific and standardized manual for the scale. A higher score indicates greater adaptive functioning.

The Vineland-3 is clinically validated for use in tracking change over time⁴⁷ and is used as an outcome measure in several randomized controlled trials for children with ASD.⁴⁸

It should be noted that the adaptive scale in question is a specific neuropsychological battery, and its content must be acquired for individual application. Therefore, its independent disclosure or copying for any purpose is prohibited. Therefore, it is not possible to include it in its entirety in this project.

4.2.9. Psychiatric Assessment

The ADOS-2 (Autism Diagnostic Observation Schedule, Second Edition) observational assessment will be applied. This is a standardized assessment that involves direct observation of the child in different situations and social interactions.⁴⁵ The evaluated parameters are divided into 5 items according to the psychiatric criteria for ASD diagnoses by the Diagnostic and Statistical Manual of Mental Disorders (DSM): language and communication; reciprocal social interaction; play and imagination; stereotypical behaviors and restricted interests and, finally, atypical behaviors. The observation lasts 60 minutes and will be carried out by trained and qualified professionals supervised by a reference neuropsychologist. This assessment has the possibility of covering children according to their language level and chronological age. Modules 1 and 2 will be aimed at children with a language level under 48 months, adapting activities such as playing with soap bubbles, using a remote-control car and pretending to have a birthday party. While module 3 will be aimed at children who can use complex sentences, as they have questions about emotions and relationships, as well as retelling a story from a book; as demonstrated in Annex B.^{45,49}

After applying the ADOS, the domains are coded on a scale that varies from 0 to 3 points, where 0 indicates that the child has a certain ability and 3 indicates abnormal or dysfunctional behavior. Higher scores indicate worse results in terms of the skills described. A standardized severity score based on codes within these domains can be calculated to compare autism symptoms between modules, according to the Standardized Manual.⁵⁰

4.2.10. Psychopedagogical Assessment

The psychopedagogical assessment will be carried out using a questionnaire validated in literature in the version translated into Portuguese, called the Childhood Autism Rating Scale (CARS).⁵¹ It consists of a scale with fifteen parameters on the symptoms of autism spectrum disorder in children, which include: interpersonal relationships, imitation, emotional response, body use, use of objects, response to changes, visual response, auditory response, response and use of taste, smell and touch, fear or nervousness, verbal communication, non-verbal communication, level of activity, level and consistency of intellectual response and finally a general parameter of that individual's autism. Because it is brief and complete, it will be answered by the teachers of each child participating in this study, in order to evaluate the possible improvement in the child's behaviors and skills also in the school context. Variations from 1 to 4, with number 1 corresponding to no difficulty in performing that skill, 2 being mild difficulty, 3 being moderate difficulty and 4 being severe difficulty. Thus, the global score varies from 15 to 60 points, and the interpretation is based on the severity of the autism; If you are

between 15 and 30 years old, you do not have autism; 30 to 36 mild to moderate autism and 36 to 60 correspond to severe autism.⁵²

4.2.11. Biostatistics

Mean and SD (standard deviation) will be used to describe quantitative data, while risk factors, frequency and percentage will be used to describe qualitative data. Shapiro-Wilk test will confirm or not the normality of data distribution in the groups, therefore, parametric, or non-parametric tests, respectively, will be used to assess the research variables. To compare quantitative variables in the two or more groups, independent t-test (between groups) or paired samples t-test (within groups), ANOVA (between groups) or Repeated Measures (within groups), with post hoc testing to assess individual differences among the categories, will be used as parametric options. The relatives nonparametric options will be used otherwise and chi square test, if qualitative variables. All statistical calculations will be performed at the significance level of less than 0.05 (P < 0.05). Data will be analyzed using SPSS version 26.0.

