2. GENERAL OBJECTIVE

The objective of this study is to evaluate the effectiveness of probiotic compounds K11-T and K11-Tmax (enriched with amino acids, minerals and vitamins), in their solid and nanoencapsulated formulations, in improving neuropsychological, psychiatric and psychopedagogical outcomes, as well as reducing inflammatory parameters in children with ASD.

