3. SPECIFIC OBJECTIVES

- Characterize the sample of individuals with ASD who will participate in the study through a questionnaire with sociodemographic and pedagogical data such as: Age in years; gender in percentage terms of the sample according to female or male; Weight in kg; Height in centimeters; Time since diagnosis of ASD in years and presence of psychiatric or neurological comorbidities in percentage terms of the sample.

- Investigate the association between probiotic consumption and neuropsychological results using the scale unit validated in the literature Vineland Adaptive Behavior Scales - Third Edition (Vineland-3) in the questionnaire format answered by parents/guardians of the child with ASD;
- Investigate the association between probiotic consumption and the change of psychiatric parameters through the application of the validated Autism Diagnostic Observation Schedule (ADOS) scale with children with ASD;
- Investigate the association between probiotic consumption and the change of psychopedagogical parameters using the Childhood Autism Rating Scale (CARS) validated in the literature, which will be answered by the teachers responsible for each child participating in the study;
- Analyze the possible effect of probiotics on inflammatory aspects in individuals with ASD, through serum (Insulin, C-Reactive Protein, Prolactin and Cortisol) and fecal (fecal calprotectin) biomarkers;
- Analyze the difference of using the K11-Tmax version, enriched with supplements, on the neuropsychological, psychiatric and psychopedagogical outcomes described above in comparison to the group that used K11-Tmax alone with the presence of a control group that will receive placebo.

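### Mean and SD are fixed for all quantitative data even where the plan's own normality rule selects a rank test, so strongly skewed biomarkers would have no summary that matches their P-value

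*Protocol*

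**What the plan says.** Protocol section 4.2.11 (Biostatistics) sets one description for every quantitative variable: "Mean and SD (standard deviation) will be used to describe quantitative data". It then makes the test depend on the data: "Shapiro-Wilk test will confirm or not the normality of data distribution in the groups, therefore, parametric, or non-parametric tests, respectively, will be used". For variables that fail, "The relatives nonparametric options will be used otherwise"; these tests are not named. No median, quartile, geometric mean or log transformation appears anywhere in the protocol.

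The general objective (section 2) includes "reducing inflammatory parameters in children with ASD", and section 3 says this will be examined "through serum (Insulin, C-Reactive Protein, Prolactin and Cortisol) and fecal (fecal calprotectin) biomarkers". These are concentrations and cannot be negative. Calprotectin, for example, is "processed using a specific kit for measurement, and expressed in µg/g" (section 4.2.7). Section 4.2.1 schedules the markers for Day 0, Day 45 and Day 90, and names Vineland-3, ADOS and CARS, not the biomarkers, as the primary outcomes.

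**The concern.** The description is unconditional and the test is conditional. When the normality rule moves a biomarker to the non-parametric route, the table would show arithmetic means and SDs beside a P-value that does not test those means. With strong right skew, the mean is imprecise and depends heavily on a few high values. The rank test, in turn, yields a P-value but no size of reduction. A reader who wants to know how far an inflammatory marker fell would have only the means to go on.

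This is a rule that the protocol states, not a detail left for a statistical analysis plan. What is at stake is the interpretability and precision of the biomarker results.

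**Working it through.** **Inputs from the protocol.** Target of 270 children (section 4) allocated 1:1:1 (section 4.2.1): 270 / 3 = 90 per arm. Minimum calprotectin subsample of 30% (section 4.2.7): 0.30 × 270 = 81, which reproduces the stated figure. If balanced, 81 / 3 = 27 per arm. Significance level 0.05 (section 4.2.11), taken as two-sided.

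**Assumptions, not in the protocol.** Biomarkers are lognormal with log-SD *s*. The range *s* = 1.0 to 1.5 is taken as plausible for C-reactive protein and calprotectin, and *s* = 0.5 as a mild case, possibly the hormones.

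**Step 1: would the normality rule switch to a rank test?** In simulation, Shapiro-Wilk rejects in at least one of three arms in 71% of trials at *s* = 0.3 and 96% at *s* = 0.5 with 27 per arm, and in at least 99.6% with 90 per arm. With truly normal data the figure is about 15%. The switch is conditional, but likely even under moderate skew.

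**Step 2: how far is the mean from the centre?** Mean/median = exp(*s*²/2): 1.13 at *s* = 0.5 and 1.65 at *s* = 1.0. At *s* = 1.0, the single largest of 27 values carries about 18% of an arm's total, and the four largest of 90 carry about 23%. Under normality these shares are 5% to 6%.

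**Step 3: precision.** For a ratio between arms, the large-sample variance per arm is (exp(*s*²) − 1)/n for the log of the arithmetic mean and *s*²/n for the log of the geometric mean. Relative efficiency = *s*² / (exp(*s*²) − 1).

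| *s* | Calculation | Efficiency |
|---|---|---|
| 0.5 | 0.25 / 0.284 | 0.88 |
| 1.0 | 1 / 1.718 | 0.58 |
| 1.5 | 2.25 / 8.488 | 0.27 |

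At 90 per arm, arithmetic means are therefore about as precise as geometric means from 0.58 × 90 ≈ 52 children per arm (*s* = 1.0) or 0.27 × 90 ≈ 24 (*s* = 1.5).

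**Step 4: agreement between summary and test.** Simulation with a true 30% reduction (ratio 0.70) and 90 per arm, looking only at trials where the rank test is significant in favour of the active arm:

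- A t-test of raw means is non-significant in 31% to 35% of these trials at *s* = 1.0 and 62% to 65% at *s* = 1.5, across repeated runs.
- A t-test on the log scale is non-significant in only 3% to 4% and 7% to 8%.
- The mean difference has the opposite sign to the significant rank test in about 0.1% to 5% (highest value in any run 5.5%).
- At *s* = 0.5, the raw t-test disagrees in about 0.3% of trials.

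**The case against.** Several objections stand and limit the point.

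- A reader might infer that the biomarkers will be rank-tested and that the reported effect will be a difference of means. The text supports neither as a certainty. The rank test depends on Shapiro-Wilk, the quoted sentence governs description, and the protocol defines no effect estimate.
- The plan would not run a raw t-test beside a rank test on the same variable. The 31% to 65% figures therefore show how poorly the mean reflects the rank result; they are not two P-values that would be printed together.
- A reader might infer that the means would often point the wrong way. Over all simulated trials at 27 per arm, the arithmetic mean difference has the wrong sign in 14% (*s* = 1.0) to 28% (*s* = 1.5), against 9% to 19% for geometric means. Low power drives much of this: the rank test has 24% and 13% power there. A difference of medians does little better than means (14% and 24% against 15% and 27% in one run). Beside a significant rank test the wrong sign is rare.
- Lognormality and the log-SD range are assumed. The figure of 27 per arm assumes the minimum subsample and an equal split of a convenience sample.
- Effect measures and transformations are often left to a statistical analysis plan, and section 4.2.11 does not forbid adding medians. That is fair for what is merely absent. It does not cover an unconditional summary rule that sits badly with the test rule in the same paragraph.

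**Conclusion.** The mismatch is real and is fixed in the text: mean and SD apply to all quantitative data, including variables that the plan itself would judge non-normal. For strongly right-skewed biomarkers, the only summary fixed is imprecise, leans on a few high values and does not correspond to the rank-test P-value, which itself gives no size of reduction. Under the lognormal assumption, the arithmetic mean keeps about 58% of the information at log-SD 1.0 and 27% at 1.5. At log-SD 0.5 it keeps about 88%, so little is lost for mildly skewed markers.

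The weight is minor to moderate. Reduced inflammation is part of the general objective, but the biomarkers are not among the named primary outcomes. Neither type I error nor the analysis of the primary scales is affected.

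**What to change.** In section 4.2.11, state in advance that C-reactive protein and fecal calprotectin, and any other biomarker expected to be clearly skewed, are analysed on the natural-log scale. Compare arms with the log Day 0 value as covariate, and report ratios of geometric means (percent differences) with 95% CI. Add a pre-stated rule for values below the assay limit; half the limit is one workable convention. Describe these variables by geometric mean, or by median and quartiles, and keep mean and SD for variables treated as normal. For the markers so named, the pre-set scale replaces the data-dependent switch.

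The cost is a few sentences and a log transform in SPSS. The Day 0 values are already scheduled, so no new data are needed. The small downside is that results read as percent differences and not in assay units.

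### Between-arm tests ignore the Day 0 score and the stratification factors, and within-arm tests stand beside them unranked; a baseline-adjusted Day 90 contrast would cost almost nothing

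*Protocol*

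**What the plan says.** Protocol section 4.2.1 names three primary outcomes, "for the primary outcomes mentioned in this project: neuropsychological (Vineland-3); psychiatric (ADOS) and psychopedagogical (CARS", each assessed on Days 0, 45 and 90. Allocation follows baseline: "After the first data collection, individuals will be randomized to receive" one of two probiotics or placebo, 1:1:1. It also states: "Children will be stratified by age, gender and level of support (see Appendix B) and then randomized". Section 4 sets the size, "with a target of 270 volunteer participants with ASD", which is 90 per arm.

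Section 4.2.11 then fixes the tests. The sentence opens "To compare quantitative variables in the two or more groups" and lists "independent t-test (between groups) or paired samples t-test (within groups), ANOVA (between groups) or Repeated Measures (within groups", with post hoc tests. The choice between these and rank-based counterparts is made on the trial data: "Shapiro-Wilk test will confirm or not the normality of data distribution in the groups". One threshold covers everything: "All statistical calculations will be performed at the significance level of less than 0.05".

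Neither this section nor any other names a covariate, a baseline adjustment or a stratified analysis. Section 4.2.11 does not say whether the between-arm tests use Day 90 scores or change from Day 0, nor which test decides efficacy.

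**The concern.** Four features of section 4.2.11 bear on how well the randomised comparison is made.

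1. **Baseline is unused.** A child's Day 0 score normally predicts the Day 90 score. Leaving it out of the between-arm test leaves explainable variance in the error term.
2. **Strata are unused.** Stratified allocation balances the arms on age, gender and support level. If Day 90 scores are compared without those factors, the standard error is too large for the balanced design and the test is conservative.
3. **Within-arm tests are not ranked below between-arm tests.** A paired test inside one arm does not test the randomised comparison, and children may improve in every arm, placebo included. Repeated measures is itself labelled as within groups. The opening of the sentence suggests that an arm-by-time model may have been meant, but none is stated.
4. **A normality pre-test picks the analysis.** The data then decide whether a mean difference or a rank comparison is reported.

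At stake are the precision of the main result, for the same 270 children, and the clarity of which result counts.

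**Working it through.** **Inputs from the protocol.** 270 children at 1:1:1, so 90 per arm (sections 4 and 4.2.1); threshold 0.05 (section 4.2.11).

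**Assumptions.** Two-sided tests; 80% power; no dropout; Day 0 to Day 90 correlation r = 0.5, 0.7 or 0.8; equal SD at both visits. The protocol gives no effect size, SD, power or correlation. It therefore has no detectable difference to reproduce, and the prevalence behind its 270 is not stated.

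**1. Detectable difference.** The noncentral t with 90 per arm gives d0 = 0.420 SD for Day 90 scores. The other analyses scale it:
- change score: d0 × √(2(1 − r))
- ANCOVA: d0 × √(1 − r²)

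| | r = 0.5 | r = 0.7 | r = 0.8 |
|---|---|---|---|
| Day 90 score (SD) | 0.420 | 0.420 | 0.420 |
| Change score (SD) | 0.420 | 0.325 | 0.266 |
| ANCOVA (SD) | 0.364 | 0.300 | 0.252 |
| Variance cut by ANCOVA vs Day 90, r² | 25% | 49% | 64% |
| Variance cut by ANCOVA vs change, (1 − r)/2 | 25% | 15% | 10% |
| Per arm to match ANCOVA, Day 90 scores | 120 | 176 | 250 |
| Per arm to match ANCOVA, change scores | 120 | 106 | 100 |

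In points at r = 0.7, for an assumed SD of 10, 15 (the Vineland-3 normative value in section 4.2.8) or 20:
- Day 90 scores: 4.2, 6.3 or 8.4
- change scores: 3.3, 4.9 or 6.5
- ANCOVA: 3.0, 4.5 or 6.0

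**2. Power for a true 0.30 SD.**

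| | r = 0.5 | r = 0.7 | r = 0.8 |
|---|---|---|---|
| Day 90 score | 52% | 52% | 52% |
| Change score | 52% | 73% | 89% |
| Arm-by-time F test, 3 arms × 3 visits, 4 df | 42% | 66% | 85% |
| ANCOVA | 64% | 80% | 92% |

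The arm-by-time row assumes compound symmetry, with half the effect at Day 45 and all of it at Day 90, in one or both active arms.

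**3. Strata ignored, Day 90 scores.** If the strata explain a share R² of the variance, the true type I error is 2(1 − Φ(1.96/√(1 − R²))). This is 3.9%, 2.8% and 1.9% at assumed R² = 0.1, 0.2 and 0.3. A simulation (12 assumed strata, blocks of 6, r = 0.7, 8,000 runs) gave 3.7%, 3.1% and 2.2%. Change scores gave 5.2%, 4.8% and 4.8% when the strata affect both visits equally, so they lose nothing material.

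**4. Within-arm tests read as efficacy.** Assume no treatment effect and the same improvement dz (mean change divided by SD of change) in all three arms. With p the power of a paired t-test at n = 90, the chance that at least one active arm is significant while placebo is not is (1 − (1 − p)²)(1 − p).

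| dz | 0.1 | 0.2 | 0.3 | 0.4 | 0.5 |
|---|---|---|---|---|---|
| p | 0.155 | 0.467 | 0.804 | 0.964 | 0.997 |
| Misleading pattern | 24% | 38% | 19% | 4% | 0.3% |

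With q = 1 − p the expression is q − q³, whose maximum is 38.5%.

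**5. The normality gate.** Assume that failure in any one of three arms triggers the switch. With normal data it switches in 1 − 0.95³ = 14% of data sets. By simulation (8,000 runs) it switches in 41–42% at skewness 0.3 and 75–76% at 0.5. Type I error was 5.0%, 5.2% and 5.4% at skewness 0, 0.3 and 0.5, the same as for the plain t-test. Power at 0.42 SD was 79.8%, 79.0% and 80.3%, against 80.2%, 79.4% and 80.3%. The gate does no error-rate harm here.

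**The case against.** The strongest reply is that section 4.2.11 is a short menu of test families, and that covariates and model form belong in an SAP that is not at hand. That would answer a complaint of silence. But the section names its tests and a rule for switching between them, and an SAP using ANCOVA would depart from it.

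Second, the larger gains are measured against Day 90 scores, which the protocol does not say it compares. Section 3 speaks of change for ADOS and CARS, though of results for Vineland-3. This stands in part. If change scores are used, the gain at r = 0.7 is 73% to 80% power, or about 0.4 points at SD 15 (4.9 − 4.5), and the strata argument falls away. At r = 0.5 the gain is still 52% to 64%. Below 0.5, change scores do worse than raw scores.

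Third, nothing says that within-arm significance will count as efficacy, and the trial is described as placebo-controlled. That is right: the 38% is what the wording permits, not what it plans, and it nearly vanishes when improvement is large.

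Fourth, Vineland-3 is already age-standardised, and what the strata add once Day 0 is in the model has not been quantified. That also stands.

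**Conclusion.** The concern holds, as an efficiency and clarity point rather than a validity error. The unadjusted between-arm tests are valid, but they discard information that the trial collects anyway. Over assumed correlations of 0.5 to 0.8, adjusting for Day 0 cuts variance by 25–64% against Day 90 scores and by 25–10% against change scores. The gain shrinks to nil as the correlation nears zero. The loss is then only a few residual degrees of freedom: from 267 to 262 with baseline, age, gender and two for support level, which moves the critical t from 1.9689 to 1.9691.

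The within-arm listing matters more for interpretation, because those tests do not address the randomised comparison and nothing subordinates them. Its harm is conditional on how they are read. The normality gate affects which effect measure is reported, not error rates. The change should be made. Confidence in its size is medium, because the protocol gives neither the correlation nor the SD.

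**What to change.** In section 4.2.11:

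- For each primary outcome, make the Day 90 difference from placebo, with 95% CI, the deciding between-arm contrast. Estimate it by ANCOVA or a mixed model with the Day 0 score, age, gender and level of support as covariates.
- Fix the form of those covariates in advance. The age bands are not given, and fully crossed strata could leave small cells, so main effects are the economical choice.
- Label all within-arm tests descriptive.
- If repeated measures was meant as an arm-by-time model, say so.
- Drop the Shapiro-Wilk gate in favour of this pre-specified model plus one rank-based or robust sensitivity analysis.

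The cost is a few sentences and slightly more analysis work. Day 0 scores and stratification factors are already collected, so no extra children, visits or measurements are needed.
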